The orexin 1 receptor antagonist SB-334867 attenuated heroin SA in adult rats and diminished cue-induced, but not prime-induced, reinstatement of heroin-seeking behavior following extinction (Smith and Aston-Jones 2012). Also, orexin 2 receptor antagonists reduce heroin intake in long-access (12 h), but not short-access (2 h), SA paradigms (Schmeichel, Barbier et al. 2015). Orexin 1 receptor antagonists attenuate morphine withdrawal symptoms in rats (Azizi, Mirnajafi-Zadeh et al. 2010, Laorden, Ferenczi et al. 2012). Dual orexin antagonists seem to be particularly well suited to treating OUD. Han et al., (2020) reviewed all similar studies and found that there is evidence from multiple animal models of opioid addiction supporting the use of orexin 1 and 2 receptor antagonists to reduce addictive behaviors. Matzeau and Martin-Fardon et al., (2020) evaluated orexin 1 antagonist SB-334867 and TCSOX229 an orexin 2 receptor antagonist in rats with an oxycodone self-administration model showing that the orexin 1 receptor antagonist suppressed self-administration but not the orexin 2 receptor antagonist.

As a first step in evaluating the potential for use of the orexin 1 and 2 receptor antagonist lemborexant as an adjunctive treatment for opioid use disorder in patients in MAT with buprenorphine, we propose a phase 1b/2a drug-drug interaction study examining two doses of lemborexant as an add-on to buprenorphine-naloxone

with 18 participants (12 treated with lemborexant and 6 treated with placebo. The lemborexant group will have two lab sessions each; one with each dose of med). All participants will be currently stable in MAT treatment with buprenorphine and have symptoms of insomnia as measured by the Pittsburgh Sleep Quality Index. This is parallel groups ascending dose study.

Specific Aims:

Primary: Aim 1: To examine safety-tolerability and drug-drug interactions between lemborexant and buprenorphine-naloxone in participants with opioid use disorder and insomnia who are in MAT with buprenorphine-naloxone.

Secondary: Aim 2: To examine lemborexant for an early signal of efficacy (anticraving, anxiolysis, impulsivity, and reduced subjective withdrawal symptoms) in participants with opioid use disorder and insomnia who are in MAT with buprenorphine-naloxone.

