The primary risks occur during administration of lemborexant with buprenorphine-naloxone. This will take place on the clinical research unit, under supervision of providers and trained nursing staff who will immediately respond to any adverse event. Participants will spend the night on the CRU prior to lemborexant administration to ensure that they do not take any additional drugs or medications that could interact with lemborexant.

The identification of effective treatments for opioid use disorder would be a great benefit to society.

If any Psychiatric or non-Psychiatric medical illness (other than substance abuse) is discovered during the study, subjects will be referred for additional treatment in the community.

STUDY DESIGN

Overview

We propose a series of experiments to study the safety and target engagement of lemborexant when combined with buprenorphine-naloxone for opioid use disorder.

Study Design: Pharmacokinetic safety and pharmacodynamic efficacy signal trial of combined lemborexant and buprenorphine-naloxone (see Figure 1 below).

STUDY OVERVIEW/SCHEMA

[figure not shown]

Figure 1. Overall Study Design

Participants will include 18 individuals (goal of 9 male and 9 female) with opioid use disorder in medication assisted treatment who are a buprenorphine-naloxone sublingual film daily dose ranging from 8mg/2mg to 24mg/6mg or buprenorphine sublingual tablet dose ranging from 5.7mg/1.4mg to 17.1/4.3 once daily at the VCU MOTIVATE or other outpatient treatment setting who complete at least one drug-drug interaction treatment session with primary endpoint data (at least 12 lemborexant treated participants and 6 placebo treated subjects).

After a complete screening including the phenotyping assessment battery (PhAB) described in detail below,

participants will be randomized to either lemborexant (12 participants) or placebo (6 participants) and will undergo safety and PK testing on the CRSU at VCU, as described in Tables 1 and 2 below. We will characterize the pharmacokinetic (PK) and pharmacodynamic (PD) profiles of the combined administration of lemborexant with buprenorphine-naloxone including the time to onset, duration of action, magnitude of effects, and the pharmacokinetic disposition of buprenorphine and its major metabolite in plasma.

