Study Hypotheses: 1. *Adjunctive lemborexant (compared to placebo) will not alter the PK of buprenorphine-naloxone significantly, nor will it alter the pharmacodynamic properties related to safety (e.g., ECG, pulse oximetry changes, capnography, significant increases in sedation and agitation).* **Secondary hypotheses:** 2. *Adjunctive lemborexant will reduce subjective opioid craving, anxiety, opioid withdrawal, and impulsivity).* **Exploratory hypotheses:** 3. *Adjunctive lemborexant will not affect central mu opioid receptors as measured by pupillometry, but will increase subjective sleep ratings and behavioral effects of lemborexant will be related to behavioral profile measures from the NIDA phenotyping battery.*

Brief description of the protocol: The overall goal of this project is to develop initial human data for lemborexant combined with buprenorphine-naloxone on safety (e.g., interactive effects on cardiovascular and respiratory function, and agitation and sedation) and efficacy (subjective craving and anxiety, opioid withdrawal and impulsivity) in opioid use disorder participants. The sample will be recruited from VCU MOTIVATE clinic and other treatment programs and consist of participants with opioid use disorder of at least moderate severity that have been stabilized on buprenorphine-naloxone sublingual film daily dose ranging from 8mg/2mg to 24mg/6mg or buprenorphine sublingual tablet dose ranging from 5.7mg/1.4mg to 17.1/4.3 once daily.

PRIMARY Endpoints:

1. Safety: Heart rate (HR), blood pressure (BP), respiration (pulse oximetry, end tidal CO₂ (EtCO₂), respiratory rate), agitation and sedation (Richmond Agitation Sedation Scale).
2. Buprenorphine PK: Plasma concentration-time profiles of buprenorphine and its metabolite norbuprenorphine
3. Lemborexant PK: Plasma concentration-time profiles of lemborexant and its major metabolite M10.

SECONDARY Endpoints:

1. Subjective effects on opioid craving, anxiety and lemborexant drug liking as measured by a visual analog scale (VAS), and Brief Substance craving scale (BSCS), and opioid withdrawal based on the Subjective Opioid Withdrawal Scale (SOWS).
2. Objective opioid withdrawal based on the Clinical Opioid Withdrawal Scale (COWS).
3. Impulsivity as measured by a delayed discounting task (DDT).

EXPLORATORY Endpoints:

1. Change in pupil size as an indicator of central nervous system mu-opioid pharmacological effects (Rollins, Feiner et al. 2014, measured by pupillometry.).

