Patients will be randomly assigned to lemborexant or placebo treatment groups in a 2:1 ratio using a randomization scheme overseen by the unblinded research pharmacist, such that 18 patients complete both lemborexant dosing days.

Blinding

Due to the objectives of the study, the identity of test and control treatments will not be known to investigators, research staff, or patients. The following study procedures will be in place to ensure double-blind administration of study treatments:

- Access to the randomization code will be strictly controlled.
- Packaging and labeling of lemborexant and placebo will be identical to maintain the blind. Lemborexant concentrations will not be analyzed until the end of the study.
- The study blind will be broken on completion of the clinical study and after the study database has been locked.

During the study, the blind may be broken only in emergencies when knowledge of the patient's treatment group is necessary for further patient management. Unblinding will occur by the PI contacting the research pharmacy to break the blind in case of emergency.

Formulation of Test Product

Lemborexant 5 mg tablets (Eisai Pharmaceuticals) will be used for this study. To ensure blinding, tablets will be placed in gelatin capsules by the research pharmacist prior to administration.

Buprenorphine HCl/naloxone films will be used for this study, in unblinded fashion.

Formulation of Control Product: Gelatin placebo capsules identical to capsules that enclose the study drug will be used for placebo. Dextrose powder will be used as a filling in the capsules.

Packaging and Labeling

Each package of study drug will be labeled with the required FDA warning statement, the protocol number, a treatment number, the name of the study physician, and directions for patient use and storage.

Administration of Study Drug

Dosage/Dosage Regimen

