On PK/Safety Testing week 1 Study Day 2 lemborexant (or matching placebo) is given as 5 mg at 7:00 AM after an overnight stay on the CRU. On PK/Safety Testing Week 2 Study Day lemborexant (or matching placebo) is given as 10 mg at 7:00 AM. Subjects will be continuously monitored on the CRU for 8 hours after the lemborexant dose, which is past the C_{max} lemborexant concentration, which will occur between 8:00 AM and 10:00 AM. Blood samples for determination of buprenorphine concentration and its major metabolite norbuprenorphine and lemborexant and its major metabolite M10 will be collected pre-dose and specified timepoints during the hospital stay (Table 3). Plasma levels will be utilized to determine AUC (area under the concentration–time curve from Time 0 post-dose to infinity) and $T_{1/2}$ (apparent terminal half-life) using noncompartmental analysis, and C_{max} (maximum concentration), C_{24} (concentration at 24 hours post-dose), and T_{max} (time to C_{max}). Plasma buprenorphine and norbuprenorphine and lemborexant and M10 levels will be determined in the VCU Department of Pharmacology and Toxicology drug analysis laboratory.

Dispensing: Study drug will be dispensed by the research pharmacist and administered by the research nurse on the CRU.

Supply of Study Drug at the Site: Study drug will be provided to the CRU after an order from the study physician or nurse practitioner. Storage: At the testing facility, all lemborexant, buprenorphine, and placebo must be kept in a secure, locked storage place with access limited to authorized study personnel only.

Study Drug Accountability: All study medication will be administered on the CRU. The study staff will record an accurate accounting of each medication administered.

STUDY PROCEDURES AND GUIDELINES

A Schedule of Events representing the required testing procedures to be performed for the duration of the study is diagrammed in Tables 1-2. Prior to conducting any study-related activities, written informed consent and the Health Insurance Portability and Accountability Act (HIPAA) authorization must be signed and dated by the subject. In order to better accommodate participant schedules, PK/Safety Testing Weeks 1 and 2 may be separated by up to approximately 14 days.

Clinical Assessments:**Concomitant Medications**

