All concomitant medication and concurrent therapies will be documented during screening, CRU study days, and Follow-Up days. Dose, route, unit frequency of administration, and indication for administration and dates of medication will be captured.

Clinical Opiate Withdrawal Scale (COWS) and Subjective Opiate Withdrawal Scale (SOWS)

These scales will be administered each study day during screening, admission to the CRU, and CARI or Motivate clinic study days to determine the presence of symptoms indicative of opiate withdrawal.

Demographics

Demographic information (date of birth, gender, race) will be recorded at screening.

Medical History

Relevant medical history, including history of current disease, other pertinent history, and information regarding underlying diseases will be recorded at screening.

Physical Examination

A complete physical examination will be performed by qualified staff (MD, DO, NP). New abnormal physical exam findings must be documented and will be followed by a physician or other qualified staff at the next scheduled visit.

Table 1. Procedures by Day**OVERVIEW**

| Days -30 to Day 0 (approx.) | Day 0 Baseline buprenorphine PK | | |
|---|---|--|--|
| Screening and assessment at CARI/Motivate facility including phenotyping battery (PhAB) | Outpatient visit to CRU for baseline buprenorphine PK measurement | | |
| | PK/Safety Testing Week 1, Day 1 | PK/Safety Testing Week 1, Day 2 - Day 3 | PK /Safety Testing Week 1, Day 4-7 |
| | Admit to CRU for overnight stay, urine drug screen, vital signs, physical examination, COWS | Lemborexant 5mg or placebo plus Buprenorphine-naloxone safety including pulse oximetry, agitation and sedation, PK, pupillometry, withdrawal, impulsivity measures, and subjective effects. | Follow-up at CARI/MOTIVATE for withdrawal, impulsivity measures, subjective effects, and side effects. |
| | PK/Safety Testing Week 2, Day 1 | PK/Safety Testing Week 2, Day 2 - Day 3 | PK/Safety Testing Week 2, Day 4-7 |
| | Admit to CRU, urine drug screen, vital signs, physical examination, COWS. Also stay overnight for safety and observation. | Lemborexant 10mg or placebo plus Buprenorphine-naloxone safety including pulse oximetry, agitation and sedation, PK, pupillometry, withdrawal, impulsivity measures, and subjective effects. | Follow-up at CARI/MOTIVATE for withdrawal, impulsivity measures, subjective effects, and side effects. |

Schedule of Procedures and Assessments:

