A protocol violation occurs when the investigator fails to adhere to significant protocol requirements affecting the inclusion, exclusion, subject safety and primary endpoint criteria except when performed for participant safety. Protocol violations for this study include, but are not limited to, the following:

Failure to meet inclusion/exclusion criteria

Failure to comply with Good Clinical Practice (GCP) guidelines will also result in a protocol violation. The investigator will determine if a protocol violation will result in withdrawal of a subject.

When a protocol violation occurs, it will be discussed with the investigator and a Protocol Violation Form detailing the violation will be generated. A copy of the form will be filed in the site's regulatory binder, and these will be reported to VCU IRB and the DSMB.

DATA SAFETY MONITORING

The Data Safety and Monitoring Plan includes establishment of a Data Safety Monitoring Board who will include five individuals who are completely independent of the investigators and who have no financial, scientific, or other conflict of interest with the trial. Each member will provide written documentation attesting to absence of conflict of interest. Additionally, [name] will serve as the on site medical monitor for the study.

For full data safety monitoring information see the Data Safety Monitoring Plan.

STATISTICAL METHODS AND CONSIDERATIONS

Initial analyses will evaluate group differences on demographic and baseline variables, will use contingency tables with chi-square testing, ANOVA's, and examination of correlations between baseline variables subjective responses and clinical results. General data analysis procedures: Prior to data analysis procedures, groups will be examined for differences in baseline characteristics that could potentially influence treatment outcome. Any variables that differ between groups and are related to outcome measures will be examined as potential covariates in subsequent data analyses.

Primary outcome measures:

1. Safety: Heart rate (HR), blood pressure (BP), respiratory rate, agitation and sedation (Richmond Agitation-Sedation Scale) and pulse oximetry during a placebo dose will be compared to HR and BP after each lemborexant dose (5 mg and 10 mg doses). Changes in safety measures induced by lemborexant dose along with buprenorphine will be compared to those without lemborexant, by lemborexant dose level (5 mg and 10

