mg doses), using a generalized linear mixed model analysis with the participant as a random effect for each outcome. Adverse event data will be compiled for lemborexant and placebo cohorts and presented as summary statistics.

2. Buprenorphine PK: Plasma concentration-time profiles of buprenorphine and its metabolite norbuprenorphine after doses during the lemborexant placebo/administration (Day 0, 1, 2) will be analyzed to obtain pharmacokinetic parameter estimates of buprenorphine (Cmax, Tmax, AUC, apparent t_{1/2}, CL/F for parent buprenorphine and metabolic (AUC) ratios for metabolites) by individual. These parameters will be compared within subjects on sessions with lemborexant. Lemborexant PK will be compared with published lemborexant PK data. As it would be unethical to withhold buprenorphine treatment from patients who are on buprenorphine for MAT, there will be no lemborexant dose without buprenorphine.

3. Changes in secondary outcome measures induced by lemborexant dose along with buprenorphine will be compared to those without lemborexant, by lemborexant dose level (5 mg and 10 mg doses), using a generalized linear mixed model analysis with the participant as a random effect for each outcome.

Safety and tolerability data will be summarized by treatment group.

Adverse event rates will be coded by body system and MedDra classification term. Adverse events will be tabulated by treatment group and will include the number of patients for whom the event occurred, the rate of occurrence, and the severity and relationship to study drug.

Interim Analysis

There will be no formal interim analysis.

Rationale for sample size: Sample size for effect of lemborexant on recommendations from the FDA regarding phase I safety studies.

DATA COLLECTION, RETENTION AND MONITORING

Data Collection Instruments

The Investigator will prepare and maintain adequate and accurate source documents designed to record all observations and other pertinent data for each subject treated with the study drug.

Study personnel at each site will enter data from source documents corresponding to a subject's visit into the protocol-specific paper/electronic CRF when the information corresponding to that visit is available. Subjects will not be identified by name in the study database or on any study documents to be collected by the Sponsor (or designee), but will be identified by a subject number.

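### Hypothesis 1 compares buprenorphine PK under lemborexant with placebo, but the PK analysis names only a within-subject comparison and gives no interval, margin or meaning for 'significantly'

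*Combined protocol and SAP*

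**What the plan says.** **Hypothesis.** Study Hypotheses, item 1, states that "Adjunctive lemborexant (compared to placebo) will not alter the PK of buprenorphine-naloxone significantly, nor will it alter the pharmacodynamic properties related to safety". ECG and capnography are among its examples of the safety measures. 'Significantly' is not defined there or elsewhere.

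**PK analysis.** The synopsis (Statistics, Primary Analysis Plan) and Statistical Methods and Considerations list the buprenorphine parameters to be estimated for each individual, then say: "These parameters will be compared within subjects on sessions with lemborexant". No reference session, placebo-arm role, scale, test or interval follows. The session labels are loose. The statistics text speaks of Days 0, 1 and 2, while Pharmacokinetic Measurements places sampling on Day 0 and on Day 2 of each testing week. Tables 1 and 3 label Day 0 as the buprenorphine baseline.

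**Safety analysis.** A comparison with non-lemborexant data is named. Study Outcome Measures compares each measure, including EtCO₂, during placebo with the same measure after lemborexant. Statistical Methods specifies a generalized linear mixed model by dose level, but its opening sentence is muddled ("pulse oximetry during a placebo dose will be compared to HR and BP after each lemborexant dose") and its list omits capnography. ECG is in neither list.

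**Sequence.** The design statement in the Background reads "This is parallel groups ascending dose study". Table 1 describes Day 0 as an "Outpatient visit to CRU for baseline buprenorphine PK measurement". Under Study Drug and Dosage, the Week 1 dose "is given as 5 mg at 7:00 AM after an overnight stay on the CRU", and the 10 mg dose comes in Week 2.

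**The concern.** The hypothesis and the analysis ask different questions. A hypothesis against placebo calls for the placebo participants' data, and Table 1 sends them through the same sessions. The stated PK comparison leaves them out.

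The difference has consequences. In a ratio to Day 0 within lemborexant participants, anything that differs between the first session and later ones is counted as lemborexant: an overnight stay, familiarity with the procedures, or drift over the weeks. The 10 mg session is also always the last. The placebo arm is the only part of the design that can remove such shifts.

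Without a named contrast or reporting rule, the same PK data could be read after the fact as supporting hypothesis 1 or not. The protocol says that no data exist on this combination, so a conclusion of no alteration could be relied on later.

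**Working it through.** **1. The plan's own figure.** N = 18 is 12 + 6, which matches 2:1. It cannot be reproduced further, because no alpha, power, effect size, CV or margin is given. The synopsis bases it on the safety and PK measures and the statistics section on FDA recommendations; neither shows a calculation.

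**2. Inputs for an illustration.** From the documents: 12 lemborexant, 6 placebo, Day 0 plus one session per dose. Assumed: within-subject CV of 20, 30 or 40%; log-normal data; a two-sided 5% test; all 12 and 6 contributing at the dose concerned.

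**3. Formulas.**
- Within-subject log SD: σ = √ln(1 + CV²) = 0.198, 0.294, 0.385.
- One session vs Day 0 in 12 pairs: SE = σ√(2/12), df 11.
- Change from Day 0, 12 vs 6: SE = √2·σ·√(1/12 + 1/6), df 16.
- Probability of non-significance: P(|T| < t₀.₉₇₅) for a noncentral t with ncp = ln(true ratio)/SE. Critical values are 2.201 (df 11) and 2.120 (df 16); ln 1.25 = 0.2231.
- Expected 90% CI at an observed ratio of 1.00: exp(±t₀.₉₅·SE), with t₀.₉₅ = 1.796 and 1.746.

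**4. Results.**

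| Contrast | CV | SE | ncp at 1.25 | Non-significant, true 1.25 | Non-significant, true 1.50 | 90% CI at ratio 1.00 |
|---|---|---|---|---|---|---|
| 12 pairs | 20% | 0.081 | 2.76 | 29% | 0.5% | 0.86–1.16 |
| 12 pairs | 30% | 0.120 | 1.86 | 60% | 13% | 0.81–1.24 |
| 12 pairs | 40% | 0.157 | 1.42 | 75% | 35% | 0.75–1.33 |
| 12 vs 6 | 20% | 0.140 | 1.59 | 68% | 22% | 0.78–1.28 |
| 12 vs 6 | 30% | 0.208 | 1.07 | 83% | 55% | 0.70–1.44 |
| 12 vs 6 | 40% | 0.272 | 0.82 | 88% | 71% | 0.62–1.61 |

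The ratio of standard errors is √2·√(1/4)/√(1/6) = √3 = 1.73 at every CV.

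These use one session at a time. Pooling all three sessions in one model changes the 25% figures little: 25/57/73% per dose within subjects (no session effects, df 22) and 66/82/88% against placebo (with session effects, df 32).

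**5. What the extra variance buys.** Suppose the later sessions differ from Day 0 for reasons unrelated to lemborexant. The documents give no size for this, so 5% and 10% are assumed. A true ratio of 1.25 would appear within subjects as 1.25 × 0.95 = 1.19 or 1.25 × 1.05 = 1.31 at 5%, and as 1.25 × 0.90 = 1.13 or 1.25 × 1.10 = 1.38 at 10%. The placebo-adjusted ratio stays at 1.25 in expectation.

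**6. AUC window.** Study Drug and Dosage defines AUC from time zero to infinity. In Table 3, Day 0 sampling ends at 4:00, while dosing sessions add a next-morning sample. Extrapolation would therefore rest on different data in the two sessions being compared.

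**The case against.** **A within-subject contrast is defensible.** Maintenance doses differ between participants, so each person as their own control is efficient. This stands as far as it goes. The change from Day 0 keeps each participant as their own control and adds the placebo arm.

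**Day 0 is closely matched to the dosing sessions.** Table 2 puts it on the same unit with the same continuous monitoring. Table 3 gives the same buprenorphine time and the same sampling times to 4:00. A reader might infer from the outpatient label that the baseline is biased; the documents do not show that. What they show is a fixed order and no overnight stay before Day 0, so a shift is possible but of unknown size.

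**The reference can be inferred.** A reader might say that no reference exists at all. That goes too far: the Day 0 label makes it evident, though never explicit.

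**The miss rates belong to a rule the plan does not contain.** This also stands. A reader might infer that a non-significant test will be reported as no interaction, but nothing in the text says so. The rates show only what that reading would risk, and they run from 0.5% to 88% with the scenario.

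**Safety is handled better than PK.** It would be wrong to say that safety, or capnography, lacks a comparison: Study Outcome Measures names one. The remaining gaps are the inconsistent lists, ECG, and the missing interval. The numeric limits in the dose escalation and stopping section are for individual participants and do not serve as group-level margins.

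**Early-phase studies need no formal equivalence test.** Agreed; none is asked for here.

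**Conclusion.** The point holds for PK. Hypothesis 1 is stated against placebo, the analysis is stated within subjects, the placebo arm has no stated PK role, and the only criterion offered is an undefined word. In the named contrast, session and order effects cannot be separated from lemborexant.

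If non-significance were the criterion, a true 25% rise in exposure would go undetected 29–75% of the time in 12 pairs and 68–88% in 12 versus 6. These figures rest on assumed CVs of 20–40% and an assumed two-sided 5% test. They also take 12 and 6 participants at each dose. That is not assured, because the completer target is given both as those who "complete at least one drug-drug interaction treatment session with primary endpoint data" and as randomisation "such that 18 patients complete both lemborexant dosing days". That inconsistency is a separate matter.

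None of this shows that the sample size is wrong for a study seeking initial human data. It should be fixed in the analysis plan before unblinding.

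**What to change.** 1. **Name the PK contrast.** For buprenorphine and norbuprenorphine AUC and Cmax, analyse on the log scale. For each dose, report the change from Day 0 in lemborexant versus placebo as a geometric mean ratio with a 90% CI. Make this the contrast for hypothesis 1 as worded, with the within-subject ratio to Day 0 and its 90% CI alongside. Alternatively, make the within-subject ratio primary, reword the hypothesis to match, and state that session effects are assumed absent.
2. **Fix the AUC window.** Use the sampling common to all sessions, from the pre-buprenorphine sample to 4:00, or state the extrapolation rule.
3. **State the reading rule.** A non-significant test will not be read as absence of interaction. Any such claim requires the CI to lie within a margin that the sponsor justifies in advance. Otherwise word hypothesis 1 as estimation and give the expected CI width under stated CVs.
4. **Align the safety lists.** Bring the synopsis and Statistical Methods into line with Study Hypotheses and Study Outcome Measures by adding EtCO₂ and named ECG measures. Report model-based differences with confidence intervals at a stated level.

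**Cost.** Wording only: no new participants, visits or samples. The price is precision. At an assumed CV of 30% and an observed ratio of 1.00, the placebo-adjusted 90% CI would be about 0.70–1.44, against 0.81–1.24 for 12 pairs. A formal no-interaction claim will often be out of reach, and the usual result will be an estimate with its uncertainty.
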